10.5.5 Karnofsky Performance Status

Karnofsky performance status scores will be summarized at each assessed time point. The change in scores from baseline to each assessed time point and from baseline to safety follow-up will also be summarized.

10.5.6 Physical Measurements

The change in weight from baseline to each scheduled assessment time point will be summarized.

10.5.7 Antibody Formation

Positive anti-AMG 211 anti-body data will be listed and reviewed for each subject. Summaries of positive anti-AMG 211 anti-body test results over time may be provided.

10.5.8 Exposure to Investigational Product

Descriptive statistics will be produced to describe the exposure to investigational product by dosing schedule. The number of cycles, number of doses of investigational product and the total dose in μg will be summarized.

Details for each AMG 211 administration will be listed for every subject. In addition a listing of the unique manufacturing lot numbers, and a listing of the subjects administered each manufacturing lot number will be provided.

10.5.9 Exposure to Concomitant Medication

All medication will be coded using the WHO drug dictionary. A subject listing of all prior and concomitant medications will be presented.

10.6 Efficacy Analyses

Statistical analyses of efficacy endpoints will be considered exploratory. Efficacy data will be conducted on the Safety Analysis Set. Dose/exposure-response relationship may be explored graphically.

10.6.1 Disease Response Analyses

All disease response data will be reported descriptively in the form of listings for all subjects. Listings will be produced for all subjects in the dose-escalation cohorts and the dose-expansion cohorts indicating the time to progression, objective response, time to response, and duration of response.

Unscheduled tumor assessments will be included in the response classifications for any analysis incorporating disease response data.

10.6.2 Best Overall Response

The number and percentage of subjects with a best overall disease/tumor response of complete response (irCR), partial response (irPR), stable disease (irSD) or progressive disease (irPD) will be presented for the dose escalation and/or expansion parts of the study. Subjects with best overall response of irSD should meet a minimum duration of 8 weeks at the time of scan.

In addition, the proportion of subjects treated at MTD with an overall response (ORR) and corresponding exact 80% confidence interval calculated using the Clopper-Pearson method ([Clopper and Pearson, 1934](#)) will be tabulated. Unevaluable subjects treated at MTD will be treated as non-responders and included in the calculation of ORR.

10.6.3 Time to Progression

Kaplan Meier curve will be presented for time to tumor progression with estimates for rates and 80% CI at selected weeks. Subjects treated at MTD will be included for this analysis.

10.6.4 Progression Free Survival

The proportion of subjects that are progression free at 6 months with corresponding exact 80% CI will be calculated using the Clopper-Pearson method. Subjects treated at MTD will be included for this analysis.

Kaplan Meier curve will also be presented as a sensitivity analysis with estimates for rates and 80% CI if subjects come off study prior to 6 months for reasons besides disease progression.

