3.5.1 Study Duration for Subjects

It is anticipated that an individual subject will participate in the study for approximately 8 months including a screening period lasting 21 days, a treatment period lasting approximately 4 to 6 months, and a safety follow-up period lasting approximately 4 weeks. The actual duration for individual subjects will vary depending upon tolerability of AMG 211, evidence of clinical progression, and willingness to participate in the study.

In the event that a subject demonstrates clinical benefit from therapy, he or she may continue treatment with AMG 211 until he or she experiences an unacceptable adverse

event, confirmed disease progression per modified irRC ([Appendix D](#)), or he or she wishes to withdraw consent. Due to the mechanism of action of immune-enhancing therapies, subjects may experience infiltration of T cells in existing lesions leading to an apparent enlargement of existing lesions or the appearance of new lesions prior to maximal clinical benefit of AMG 211. The decision to continue on the study should be made by the treating physician and the subject.

End of study (EOS) for an individual subject is defined as the date of the final study visit (EOS visit) when safety assessments and procedures are performed. The EOS visit should occur approximately 4 weeks (+ 1 week) after the last dose of AMG 211 or at the initiation of other therapy. Subjects who complete the EOS visit will be considered to have completed the study.

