Percent change from Baseline is the arithmetic difference between post-Baseline and Baseline divided by Baseline values times 100.

Progression-Free Survival Time

Progression-free survival time is calculated as the number of days from the first administration of AMG 211 to the first assessment of disease progression as per modified irRC or clinical progression, whichever occurs first or death due to any cause, or if applicable date of censoring (date of progressive disease or death or censoring – date of study day 1 +1). Progression-free Survival Time will incorporate the independent radiologic review and/or the Investigator-reported assessment. The progression-free rate at 6 months is defined as the proportion of subjects with no disease or clinical progression at 6 months from the first administration of AMG 211.

The following censoring strategies for missing assessment dates will be used for the progression free survival analysis:

If a subject's disease has not progressed and the subject is alive, progression-free survival time will be censored at the last date they are known to be progression-free (ie, the last evaluable radiological assessment date).

If a subject has no tumor evaluation in the study, progression-free survival time will be censored at the date of the first administration of AMG 211.

Subjects who withdraw consent to participate in the study prior to disease progression will be censored at their last evaluable radiological assessment date.

Screened

A subject is considered in screening once a consent form has been signed.

Study Day

Post study day 1: study day= (date - date of Study Day 1) + 1

Pre study day 1: study day= (date – date of Study Day 1)

Study Day 1

Study day 1 is defined as the first day of administration of the investigational product after enrollment. The day prior to Study Day 1 is considered Day -1.

Treatment-Emergent Adverse Event (TEAE)

A treatment-emergent adverse event is any adverse event starting on or after the first dose of investigational product, as determined by the flag indicating if the adverse event started prior to the first dose on the Adverse Events Summary CRF, and up to and including 30 days after the end of investigational product.

Treatment-Related AE

A treatment-related AE is any treatment-emergent AE that per investigator review has a reasonable possibility of being caused by the investigational product.

Time to Progression (TTP)

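### The main 6-month progression-free rate is a crude proportion with no rule for subjects who leave unprogressed before month 6; the Kaplan-Meier estimate already planned should take its place

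*SAP*

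**What the plan says.** The 6-month progression-free rate is a named secondary endpoint (Protocol 10.1.1, SAP 4.2). Its main estimate is the same in SAP 10.6.4 and Protocol 10.4.3.3: "The proportion of subjects that are progression free at 6 months with corresponding exact 80% CI will be calculated using the Clopper-Pearson method". SAP 10.6.4 limits the analysis to subjects treated at the MTD.

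SAP section 6 defines the quantity: "The progression-free rate at 6 months is defined as the proportion of subjects with no disease or clinical progression at 6 months", counted from first dose. The censoring rules in the same entry are written for progression-free survival time. The proportion has no rule of its own for a subject whose follow-up ends before month 6.

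SAP 10.6.4 then adds: "Kaplan Meier curve will also be presented as a sensitivity analysis", to be done "if subjects come off study prior to 6 months for reasons besides disease progression". The protocol plans Kaplan-Meier for time to progression but not for this rate.

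On follow-up, Protocol 3.5.1 expects "a treatment period lasting approximately 4 to 6 months" and states: "The EOS visit should occur approximately 4 weeks (+ 1 week) after the last dose of AMG 211", or when other therapy begins. A subject who attends that visit has completed the study. Protocol 7.2.4 and 7.3.6 ask for a scan at that visit if the last one is at least 6 weeks old and progression has not been confirmed.

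**The concern.** A binomial proportion needs a yes or no for every subject at month 6, and the follow-up schedule does not always supply one. Protocol 8.3.1 lists reasons for stopping treatment other than progression, such as subject request, a safety concern or a sponsor decision. A subject who stops in month 3 for such a reason can be finished with the study by about month 4. The end-of-study scan gives the status then, not at month 6.

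The analyst must put this subject in the numerator, only in the denominator, or nowhere. Each choice biases the rate, and not all in the same direction. If the choice is made after the data are seen, the headline figure depends on a rule that nobody wrote down. The SAP foresaw the situation, since it is the trigger for the Kaplan-Meier analysis, but kept the estimator that cannot handle it as the main one.

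**Working it through.** **1. The plan's own interval method.** Neither document gives a figure for this endpoint. The nearest are the 80% Clopper-Pearson intervals for ORR. The limits are the 10th percentile of Beta(x, n−x+1) and the 90th percentile of Beta(x+1, n−x).

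- 8/39 = 20.5%: 12.3% to 31.2%, half-width 9.42 points. Protocol 10.2 states 12.3% to 31.2% and 9.5; its rounded limits give (31.2 − 12.3)/2 = 9.45.
- 2/10 = 20%: 5.5% to 45.0%, half-width 19.75 points. SAP 3.2 states 5.4% to 45.0% and 19.8.

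Both are reproduced to within 0.1 point.

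**2. Who has no month-6 status.** With 4 months of treatment, the low end of the expected range, plus about 4 weeks to the end-of-study visit, follow-up ends at about month 5. Stopping earlier ends it earlier. The group is smaller than all early leavers: clinical progression already counts as an event (SAP section 6), and a subject who declines further drug may agree to stay in the study (Protocol 8.1).

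**3. Expected value under each reading.** The documents give no drop-out or progression rate for this endpoint, so these inputs are assumptions: exponential time to progression with true 6-month rate S, and independent exponential drop-out with probability d by month 6 if progression did not intervene. With 6 months as the time unit:

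- λ = −ln S and μ = −ln(1 − d)
- known progression-free at month 6: K = S(1 − d)
- left unprogressed before month 6: L = [μ/(λ + μ)](1 − K)
- leavers as successes: K + L; excluded: K/(1 − L); as failures: K
- Kaplan-Meier targets S

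For S = 0.20, λ = 1.609.

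- d = 0.15: μ = 0.1625, K = 0.170, L = (0.1625/1.772)(0.830) = 0.076
- d = 0.30: μ = 0.357, K = 0.140, L = (0.357/1.966)(0.860) = 0.156

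| Leave unprogressed | As successes | Excluded | As failures | Kaplan-Meier |
|---|---|---|---|---|
| 7.6% | 24.6% | 18.4% | 17.0% | 20% |
| 15.6% | 29.6% | 16.6% | 14.0% | 20% |

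Exclusion biases downward because some would-be leavers progress first and stay in as failures, while those who leave unprogressed are removed.

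**4. Wider range.** For true rates of 10%, 20% and 30%, with 5%, 10% and 20% leaving unprogressed, the error against the true rate is:

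- +2.4 to +15.4 points with leavers as successes
- −0.8 to −4.9 points with leavers excluded
- −1.2 to −9.9 points with leavers as failures

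**5. One data set, three answers.** Take 39 subjects, 8 known progression-free at month 6 and 4 unprogressed leavers:

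- as successes: 12/39 = 30.8% (80% CI 21.0% to 42.1%)
- excluded: 8/35 = 22.9% (13.8% to 34.5%)
- as failures: 8/39 = 20.5% (12.3% to 31.2%)

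**The case against.** The strongest reply is that SAP 10.6.4 already answers this. Its Kaplan-Meier analysis is triggered by exactly this situation, so the censoring-aware figure would appear beside the crude one. SAP 10.6 calls the efficacy analyses exploratory. SAP 10.6.2 treats unevaluable subjects as non-responders for ORR, which hints at the convention intended here. The end-of-study scan and possible continued participation shrink the affected group. The sizes above rest on assumed drop-out. The 9.5-point half-width also applies to 39 subjects, whereas the MTD set may be smaller: at the SAP's n = 10 the half-width is 19.8 points, which would dwarf most of these biases. Finally, Kaplan-Meier recovers 20% in the illustration only because drop-out was made independent of progression. Leaving for toxicity may not be independent, and scans 8 to 12 weeks apart with censoring at the last scan make the estimate coarser.

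Most of this stands, and it limits the practical effect. It does not remove the point. The reported main figure would still be the crude proportion, and the protocol has no Kaplan-Meier estimate for this rate at all. The non-responder rule is written for ORR only. One scan about 4 weeks after the last dose does not establish status at month 6 for someone who stopped in month 2 or 3.

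**Conclusion.** The main estimator ignores incomplete follow-up, and neither document says how subjects without a month-6 status enter it. The resulting bias can go either way. At an assumed true rate of 20%, with 7.6% to 15.6% leaving unprogressed, it is +4.6 to +9.6 points (leavers as successes), −1.6 to −3.4 (excluded) or −3.0 to −6.0 (failures). This rests on independent exponential drop-out and on leaving rates that the documents do not give.

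Two stronger conclusions are tempting and not supported:

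- A reader might infer that early leavers count as successes, so that the rate is overstated. The definition, phrased as absence of progression, permits that reading. It equally permits requiring a known progression-free status at month 6, which makes leavers failures and understates the rate.
- A reader might infer that a poorly tolerated dose would look more active than a well tolerated one. SAP 10.6.4 restricts the analysis to MTD subjects and plans no comparison of this rate between doses, and the model-based dose recommendations use DLTs.

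What is at stake is a secondary efficacy estimate. Dose decisions and sample size are unaffected. Changing the estimator is a cheap improvement.

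**What to change.** In SAP 10.6.4 and Protocol 10.4.3.3, make the Kaplan-Meier estimate at 6 months, with its 80% CI, the main estimate of the 6-month progression-free rate. Use the censoring rules that SAP section 6 already gives for progression-free survival time. Keep the Clopper-Pearson proportion as the sensitivity analysis, and state that every subject without a known month-6 status counts as not progression-free. That gives a conservative lower bound; it does not bracket the effect of informative drop-out. If the crude proportion is kept as the main estimate, the minimum is one sentence stating the rule before the analysis is run.

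The cost is wording in two documents. The Kaplan-Meier analysis is already planned in the SAP, so no data collection is added. The small downside is that Kaplan-Meier assumes non-informative censoring, which should be said when the result is reported.

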10.6.5 Tumor Burden

At each on-study radiological assessment, tumor burden will be derived as the sum of the products of the longest perpendicular diameters of the all index and new measurable lesions will be recorded. Baseline tumor burden will be the sum of the products of the 2 longest perpendicular diameters (SPD) of all the index lesions. The percentage change from baseline in tumor burden and percentage change from nadir will be recorded on the eCRF:

Individual subject time profiles of the percentage change from baseline will be generated for each part of the study. The initial dose group and primary tumor type will be highlighted.

For the dose escalation, the maximum percentage improvement (maximum decrease or minimum increase over the whole study) in the tumor burden will be plotted for each subject (waterfall plot). The initial dose group, primary tumor type and best overall response will be highlighted. This analysis will be repeated for subjects in the dose expansion part of the study.

In addition, summary statistics on percentage change from baseline by time point will be generated for subject treated at MTD.

10.6.6 Tumor Biopsy

Tumor biopsy data will be listed.

10.6.7 Duration of Response

Duration of response will be analyzed using the Kaplan-Meier method. Kaplan-Meier curves and median duration along with 80% CI will be presented. Subjects without an objective response are excluded from the analyses of this endpoint.

10.6.8 Time to Response

Time to response will be analyzed using the Kaplan-Meier method. Kaplan-Meier survival curves and median time along with 80% CI will be presented.

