10.2 Sample Size Considerations

It is anticipated that approximately 78 subjects will be enrolled in this study.

Approximately 39 subjects will be enrolled in the dose-escalation cohorts and approximately 39 subjects will be enrolled in the dose-expansion cohorts.

The sample size in dose-escalation cohort is determined empirically and is consistent with this type of study using a modified TPI Bayesian model design (Bailey et al, 2009; Neuenschwander et al, 2008).

Refer to [Appendix E](#) for details of the modified TPI Bayesian model, the average sample size, and other design operating characteristics.

In the dose-escalation cohorts, with 3 DLT-evaluable subjects per dose level, there is a 49% to 73% probability of observing at least 1 DLT if the true DLT rate is 20% to 35%.

In the dose-expansion cohorts, with 39 subjects there is a 86% probability of observing at least one adverse event with 5% incidence rate. In the dose-expansion cohorts, an exact 80% binomial confidence interval (CI) will be provided for the ORR. With 39 subjects and 20.5% ORR, the expected 80% CI and its half-width would be 12.3% to 31.2% and 9.5%, respectively.

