Time to progression is calculated as the number of days from the first administration of AMG 211 to the first objective assessment of disease progression as per modified irRC or if applicable date of censoring (date of progressive disease or censoring – date of study day 1 +1). Time to progression will incorporate the independent radiologic review and/or the Investigator-reported assessment.

The following censoring strategies for missing assessment dates will be used for the time to progression analysis:

If a subject's disease has not progressed and the subject is alive, time to progression will be censored at the last date they are known to be progression-free (ie, the last evaluable radiological assessment date).

If a subject has died, time to progression will be censored at the date of death.

If a subject has no tumor evaluation in the study, progression-free survival time will be censored at the date of the first administration of AMG 211.

Subjects who withdraw consent to participate in the study prior to disease progression will be censored at their last evaluable radiological assessment date.

Time to Response

Time to response is calculated as the number of days from the first administration of AMG 211 to the first objective assessment of response as per modified irRC or if applicable date of censoring (date of first response or censoring – date of study day 1 +1).

The following censoring strategies for missing assessment dates will be used for the time to response analysis:

If a subject did not respond, time to response will be censored at the latest evaluable radiological assessment date.

If a subject has no tumor evaluation in the study, time of response will be censored at the date of the first administration of AMG 211.

Tumor Burden

Tumor burden is derived as the sum of the products of the 2 longest perpendicular diameters (SPD) of all index lesions (5 lesions per organ and up to 10 total lesions) and new measurable lesions ($\geq 5 \times 5$ mm; up to 5 new lesions per organ and 10 total lesions) if any, per irRC guidelines.

- Tumor burden = $SPD_{\text{index lesions}} + SPD_{\text{new, measurable lesions}}$

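### Time to response is analysed by Kaplan-Meier over all treated subjects with non-responders censored, so the curve and its median can overstate response when some responses come late

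*SAP*

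**What the plan says.** The method is in SAP 10.6.8: "Time to response will be analyzed using the Kaplan-Meier method". The outputs follow in the same section: "Kaplan-Meier survival curves and median time along with 80% CI will be presented". The section does not restrict the population, so the general rule of SAP 10.6 applies: "Efficacy data will be conducted on the Safety Analysis Set". That set is everyone who was enrolled and received at least one dose.

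The censoring rule is in SAP section 6, under Time to Response: "If a subject did not respond, time to response will be censored at the latest evaluable radiological assessment date". For a subject with no tumor evaluation, "time of response will be censored at the date of the first administration of AMG 211". Neither rule distinguishes a subject who is still being followed from one whose progression has been confirmed, who has died or who has left the study. No competing-risk estimate is named.

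Two neighbouring sections treat non-responders differently. For duration of response, SAP 10.6.7 says: "Subjects without an objective response are excluded from the analyses of this endpoint". For the response rate, SAP 10.6.2 says: "Unevaluable subjects treated at MTD will be treated as non-responders and included in the calculation of ORR". Protocol 10.4.3.3 plans only listings for time to response, so the Kaplan-Meier analysis is an SAP addition.

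**The concern.** Kaplan-Meier assumes that a censored subject keeps the same future chance of the event as those still at risk. Here the censoring date is often set by treatment failure. SAP 3.1 continues treatment until confirmed progression, intolerance or clinically significant deterioration, and Protocol 7.3.6 ends scheduled imaging once progression is confirmed. A subject with confirmed irPD, or one who has died, has in practice no further chance to respond. The analysis nevertheless shares that subject's probability of response among those who remain.

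At stake is the response curve and its median, shown for a secondary endpoint. A reader would take the height of the curve as the proportion who respond by a given time. At a response rate near 20%, a median over all treated subjects is either not reached, and so uninformative, or is reached only because non-responders have been removed from the risk set.

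**Working it through.** **Inputs from the documents.** Protocol 10.2 plans the expansion part with "With 39 subjects and 20.5% ORR", which is 8 of 39. Protocol 7.3.6 sets scans every 8 to 10 weeks on the 7- and 14-day schedules. Protocol 2.4 reports that in the earlier short-infusion study of the same drug, 19 of 24 subjects (79%) treated at up to 3 mg/day stopped after at most two cycles because of progression.

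**Inputs assumed.** How the responses spread over scans, and how many non-responders have their last scan at each time. The documents give neither.

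**The plan's own figure.** 8/39 = 20.5%. The exact Clopper-Pearson 80% interval is 12.3% to 31.2%, half-width 9.4 points. Protocol 10.2 states the same limits and a half-width of 9.5. The base case is reproduced.

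**Illustration.** Take 39 subjects and 8 responders, 4 at scan 1 and 4 at scan 2, with c non-responders censored at scan 1. At a shared date, responses count before censoring. The number at risk at scan 2 is n2 = 39 − 4 − c, and

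1 − KM = 1 − (35/39) × (1 − 4/n2).

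| c | n2 | 1 − KM | crude |
|---|---|---|---|
| 18 | 17 | 31.4% | 20.5% |
| 20 | 15 | 34.2% | 20.5% |
| 22 | 13 | 37.9% | 20.5% |

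**The same data with leaving as a competing event.** For c = 18, the proportion still without either event after scan 1 is 17/39. Cumulative incidence is 4/39 + (17/39) × (4/17) = 8/39 = 20.5%. The factor n2 cancels, so the result is the same for every c.

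**Sensitivity to the assumed pattern.** Each row has 39 subjects and 8 responders, with counts at weeks 8, 16 and 24.

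| Responders | Non-responders, last scan | 1 − KM at week 24 |
|---|---|---|
| 8, 0, 0 | 31, 0, 0 | 20.5% |
| 5, 2, 1 | 16, 8, 7 | 32.2% |
| 2, 3, 3 | 16, 10, 5 | 49.2% |
| 4, 2, 2 | 20, 8, 3 | 53.3% |
| 2, 2, 4 | 20, 8, 3 | 64.1% |

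The first row has no bias. In the fourth, 1 − (35/39)(13/15)(3/5) = 53.3%, so a median of 24 weeks is reached although 31 of 39 subjects (79%) never respond.

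**Unscanned subjects.** If 4 of the 39 have no scan and all 8 responses fall at the first scan, 1 − KM = 8/35 = 22.9%. Censoring at first dose acts in the same direction, even without late responses.

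**On the SAP's own expansion size.** SAP 3.2 plans 10 subjects at 20%. With 2 responders, the patterns tried gave 20% (both at the first scan), 1 − (9/10)(3/4) = 32.5%, and 1 − (9/10)(1/2) = 55%.

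**The case against.** Several points against the concern are sound and limit it.

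- **The bias is conditional.** A reader might infer that the plan will always overstate response. It will not: with no responses, or with all of them at the first scan among scanned subjects, the curve equals the crude proportion. Protocol 2.2.4 reports no objective responses in the earlier study of this drug.
- **Progression does not always end the chance to respond.** Protocol 3.1 and Appendix D expect that lesions may enlarge or appear before benefit, require irPD to be confirmed at least 4 weeks later, and do not count new lesions as progression in themselves. The objection therefore covers confirmed irPD, death and leaving the study, not a first unconfirmed irPD.
- **The ORR is not wrong.** A reader might infer that the report would contradict its own response rate. The ORR is a separate exact proportion, tabulated for subjects treated at the MTD, whereas 10.6.8 has no MTD restriction. The two outputs can differ through their denominators alone.
- **Duration of response is not an inconsistency.** It is defined only for responders, so the exclusion there is unavoidable. It shows a workable model, not a contradiction.
- **Little depends on it.** SAP 10.6 calls efficacy analyses exploratory, no sample size or dose decision uses time to response, and SAP 10.6.1 lists each subject's value.

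What stands is that the planned curve and median rest on an assumption that fails for subjects whose chance to respond has ended, and that the plan gives no alternative estimate.

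**Conclusion.** The point holds as a minor one. As written, the time-to-response curve over all treated subjects is never below the cumulative incidence of response. It lies above it whenever some responses occur after non-responders have been censored. The median is then open to the same artefact; otherwise, at about 20% response, it is not reached.

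The 31% to 38% against 20.5% is an illustration. It rests on an assumed 4/4 split of responders, on 18 to 22 assumed losses at the first scan, and on one common set of 39 subjects. Other assumed patterns run from 20.5% to 64.1%, so the documents do not determine the size. The 79% early loss makes substantial early censoring plausible, but it comes from a different infusion schedule. Nothing here affects the ORR or any decision in the trial.

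**What to change.** In SAP 10.6.8 and the Time to Response definition in SAP section 6, replace the Kaplan-Meier analysis with a descriptive summary among confirmed responders: number, median and range. If a curve over all treated subjects is wanted, specify a cumulative incidence function with confirmed irPD, death and leaving the study without response as competing events. Count subjects without a scan as non-responders, in line with SAP 10.6.2, and reserve censoring for subjects still under follow-up without response at the data cut-off. Once follow-up is complete, that curve ends at the crude response proportion of the same set.

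The cost is about two sentences in the SAP. The protocol needs no change, since it promises only listings. The drawback is that the responder-only summary is descriptive and will rest on few subjects.
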